1.5 Study Rationale

The study will be conducted in compliance with the protocol, good clinical practice (GCP), The Declaration of Helsinki and the applicable regulatory requirement(s).

This is a two-phase study. Phase 1 (dose escalation) of this study will evaluate the safety and tolerability, as well as determine the recommended Phase 2 Dose (RP2D) of pamiparib. The PK profile, and the preliminary anti-tumor activity of the pamiparib will also be studied. Phase 2 of this study will further evaluate the anti-tumor activity of the pamiparib, its safety and PK profile

The study population used for Phase 2 consists of patients with advanced high grade, non-mucinous, epithelial ovarian cancer of either known deleterious or suspected deleterious germline *BRCA1/2* mutations susceptible to treatment with PARP inhibitor.

Pamiparib is a potent and selective inhibitor of PARP1 and PARP2. It showed potent PARP-trapping activity and anti-proliferative activity against a number of cell lines harboring *BRCA* gene mutations or HRD. Mutations of *BRCA1* and *BRCA2* predispose cells to increased risk of malignancies, particularly breast and ovarian cancer.

The reported prevalence of *BRCA1/2* mutations in patients with ovarian cancer varies in different studies, ranging from 10% to 20%. To date, there have been two major epidemiological researches about *BRCA1/2* mutations in China. One study included 916 patients with unselected consecutive EOC from Eastern China, with an overall mutation incidence of 16.7%, which is consistent with pervious global data (Shi et al 2017). The other study included 826 patients from 3 top cancer hospitals and 2 major tertiary hospitals in China; the prevalence rate or *gBRCA*m was determined to be 28.5% (Wu et al 2017).

Rationale for Dose Selection in Phase 1

Pamiparib has demonstrated a favorable toxicology and safety pharmacology profile in clinical and non-clinical experiments.

The starting dose for pamiparib will be 20 mg BID in this study, which is 1/3 of RP2D (60 mg BID) and 1/4 of MTD (80 mg BID) determined from the on-going FIH Phase 1 study of pamiparib in Australia.

Three dose levels of 20, 40 and 60 mg BID are planned for this dose escalation portion (Phase 1). An intermediate, not pre-defined, and not previously-evaluated dose or a less frequent dosing schedule could be evaluated in the dose escalation portion if necessary.

Rationale for Phase 2

Pamiparib is a particularly promising PARP inhibitor to study in solid tumors as it has a unique combination of attributes. It is a potent and selective inhibitor of PARP1 and PARP2. It has excellent PARP-trapping activity that is likely to be more important for anti-tumor activity than catalytic PARP inhibition. In the clinic, pamiparib has shown favorable PK properties, has been well-tolerated and achieved maximum pharmacodynamic target modulation in PBMCs at a dose level well below the RP2D (10 mg versus 60 mg BID). PK modeling predicts that the RP2D of pamiparib can achieve brain concentrations required for anti-tumor activity.

Rationale for Selection of pamiparib Dose in Phase 2

Based upon the overall safety, efficacy, and PK profile of pamiparib, the dose of pamiparib 60 mg PO BID was confirmed as RP2D using available clinical data from study BGB-290-AU-002 and the Phase 1 portion of this study. Study BGB-290-AU-002 determined the maximum tolerated dose of pamiparib to be 80 mg PO BID (160 mg/day). The dose of 60 mg BID was selected for further evaluation based on the following findings (refer to BGB-290 Investigator's Brochure):

- A linear PK profile observed up to 80 mg BID
- Similar toxicity profiles at 60 and 80 mg BID with the following exceptions:
 - Fewer patients at 60 mg BID experienced treatment-related AEs of anemia and neutropenia
 - There was a slightly higher rate of dose interruptions at 80 versus 60 mg BID for anemia and nausea
- Responses were observed across the dose range evaluated

BGB-290-102 Phase 1 study confirmed that the recommended dose for further investigation in Chinese patients was also 60 mg PO BID based on the following findings:

- AE profile observed from 15 female Chinese patients in BGB-290-102 study was generally consistent with that from BGB-290-AU-002 (Australia) study, and AEs could be managed clinically
- No DLTs and drug-related SAEs were observed across the dose range evaluated
- Average steady-state pamiparib plasma exposure (Cmax, AUC) at 60 mg BID in Chinese patients was approximately 35% higher than for Australian patients (AU-002). In summary, pamiparib is an excellent candidate to determine the effects of PARP inhibition in advanced cancers.

1.6 Benefit-Risk Assessment

Pamiparib is the investigational product with safety data gathered from non-clinical and Phase 1 clinical studies. Preliminary safety results of pamiparib from the ongoing Phase 1a clinical trial were summarized above. Patients enrolled in this clinical study using pamiparib must be closely monitored by means of reporting AEs, recording vital signs and ECGs, and conducting clinical laboratory safety tests on blood and urine, with particular attention paid to the safety profile of what is currently known. Pamiparib and other PARP inhibitors (eg, olaparib) in clinical trials have shown some side effects including fatigue, somnolence, nausea, loss of appetite, anemia and thrombocytopenia (NDA 209115 Rubraca; FDA Summary Review for Regulatory Action: Olaparib; Weil and Chen 2011). MDS and AML have been reported in a small number (<1%) of patients treated with PARP inhibitors, especially in patients harboring a germline *BRCA* mutation (FDA Summary Review for Regulatory Action: Olaparib). Patients who develop MDS and AML while on PARP inhibition therapy typically had a history of extensive previous chemotherapy and some had a history of previous cancer or bone marrow abnormalities. Patients in this study will be

monitored monthly for hematological toxicities and reports of MDS and AML will be reported as SAEs.

In Phase 1 (dose escalation), high grade non-mucinous ovarian cancer (including fallopian cancer, or primary peritoneal cancer), or TNBC, will be recruited. Even though *BRCA1* and *BRCA2* mutations are not required, enrichment of this patient population is encouraged. In Phase 2, HGOC (including fallopian cancer, or primary peritoneal cancer) patients with germline *BRCA1/2* mutation will be recruited. The PARP inhibitors, including pamiparib in clinical development, have shown clinical benefit in these patient populations.

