Four patients experienced AEs that were considered dose limiting toxicities (DLTs): 2 patients experienced Grade 2 nausea that persisted despite optimal standard medical therapy; 1 patient experienced Grade 2 anorexia and Grade 2 nausea, and 1 patient experienced Grade 2 nausea and Grade 2 paresthesia. Based on the encountered DLTs and the overall safety profile of pamiparib, the MTD of pamiparib was determined to be 80 mg PO BID (160 mg/day).

MDS or acute myeloid leukemia (AML) are recognized AEs in patients receiving PARP inhibitors (Ricks et al 2015). To date, no cases of either MDS or AML have been observed in any study that includes pamiparib.

Ten patients achieved either a complete (n=2) or partial (n=8) response; all responses were observed in patients with gynecological cancers.

Clinical Safety and Preliminary Efficacy for BGB-290-102 Phase 1 study

The Phase 1 portion of study BGB-290-102 evaluated the safety, tolerability, PK, and preliminary efficacy of pamiparib in Chinese patients with advanced high-grade, non-mucinous, epithelial ovarian cancer, including fallopian and primary peritoneal cancer, or TNBC. Three cohorts with BID dosing (20, 40, and 60 mg) were evaluated in the dose-escalation phase. Preliminary data for 15 patients are available (HGOC: n=9; TNBC: n=6; as of 25 September 2017): n=4 for 20 mg, n=4 for 40 mg and n=7 for 60 mg.

The most common related AEs were asthenia (n=12), nausea (n=12), decreased appetite (n=9), white blood cell count decreased (n=9), anemia (n=8) and neutrophil count decreased (n=7). Treatment-related Grade 3 AEs in \geq 2 patients were anemia (n=5), decreased neutrophil count and decreased white blood cell count (n=2 each). No \geq Grade 4 AEs were reported. All SAEs were not related to pamiparib (1 each of abdominal infection, ileus, and pleural effusion). No dose-limiting toxicities were reported; and the recommended Phase 2 dose was confirmed as 60 mg PO BID.

Available preliminary efficacy data for 8 HGOC patients (all platinum-resistant/refractory) showed 2 patients with partial response (on treatment: n=2; *BRCA1/2* mutation: n=1) and 4 with stable disease (on treatment: n=4; *BRCA1/2* mutation: n=2). Median duration of treatment for 9 HGOC patients was 133 days (range: 8–260). Available preliminary efficacy data for 5 TNBC patients showed progressive disease (PD) for all 5 (*BRCA1/2* mutation: n=1).

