4.1.1.3 Dose Continuation, Intra-patient Dose Escalation and Dose De-escalation

In the absence of unacceptable toxicity, disease progression, or patient withdrawal, patients may continue with BID administrations of pamiparib at the discretion of the investigator. The sponsor may consider to roll over those patients who are still on treatment and derive clinical benefit to a new study to continue receiving pamiparib treatment and follow for safety and other clinical relevant information if this study has been ended.

Intra-patient dose escalation is not allowed in this study.

In the event of a DLT, treatment will be stopped and supportive therapy administered as required. If the toxicity resolves or subsides to Grade 0, Grade 1 or Grade 2 (Grade 2 is only applicable to neutropenia) within 14 days and interruption or delay of treatment for no more than 21 days of the onset of the DLT and the patient is showing clinical benefit in the investigator's opinion, resumption of treatment after resolution of a DLT will be at the next lower dose level tested (or 50% lower if the DLT occurs with the first dose level). If the toxicity does not resolve to Grade 0, Grade 1 or Grade 2 (Grade 2 is only applicable to neutropenia) within 14 days of onset, the patient must be withdrawn from the study. Any exception to this must be agreed upon by the investigator and the medical monitor.

The visit schedule for Phase 1 portion is presented in Table 5.

Table 5.Study Visit Schedule in Phase 1 Portion

Assessments ⁶	Screening ¹			Cycle (23 da			Cycle 2 (21 days)	Cycle 3 (21 days)	Cycle 4 and Subsequent Cycles (every 21 days for 1 cycle in Year 1, every 12 weeks ± 7 days thereafter)	EOT Visit ²	Safety Follow-up ³
Day of Study	D -21 to -1	D1	D2	D3	D10	D17	D24	D45	D66~	Within 5	30 ± 5 days
Allowed time window							±2 days	±2 days		days after last dose	after last dose
Informed consent	X										
Baseline demographics	X										
Medical history/treatment ⁴	X										
Concurrent medications	X	Х			X	Х	Х	Х	Х	Х	Х
Physical examination ⁵	Х	Х			X	X	Х	Х	Х	Х	Х
Vital signs	X	Х	Х	Х	X	х	Х	Х	Х	Х	Х
Weight	X	X			X	Х	Х	X	Х	X	
ECOG performance status	X	X					Х	X	Х	X	
Hematology ⁷	X	X			Х	Х	Х	X	Х	X	
Clinical chemistry ⁷	X	Х			Х	Х	Х	Х	Х	X	
CA-125 ⁸	X]		EVERY Y 12 WI						
Coagulation		X			X	X	Х	X	Х	X	
Urinalysis ⁹	X						Х	X	Х	X	

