- 5. Full physical exam includes the following items: 1) general appearance; 2) head, eyes, ears, nose and throat; 3) neck; 4) heart; 5) chest (including lungs); 6) abdomen; 7) extremities; 8) skin; 9) lymph nodes; 10) cardio-vascular; and 11) neurological status. Only at baseline and EOT visit is the full physical examination required. In other visits (or as clinically indicated), limited symptom-directed physical examinations will be performed
- 6. All assessments, unless stated otherwise, must be performed before investigational product administration in each cycle
- 7. In the event of neutropenia (absolute neutrophil count <1000/mm³), thrombocytopenia (platelets of less than 50,000/mm³), or ≥ Grade 3 clinical chemistry toxicity, these assessments will be conducted as frequently as the physician feels needed until toxicity resolves to ≤ Grade 2
- 8. Patients with high grade epithelial tumor, non-mucinous ovarian cancer, fallopian cancer, or primary peritoneal cancer will have CA-125 tested in local laboratory within 2 weeks before the dose of pamiparib, every 6 weeks ± 7 days after the first dose of the study drug in the first year, then every 12 weeks ± 7 days thereafter. The CA-125 responses must be confirmed and maintained for at least 28 days. Patients can be evaluated according to CA-125 only if they have a pretreatment sample that is at least twice the upper limit of reference range and within 2 weeks before starting the treatment
- 9. If urine protein is $\geq 2+$, a 24-hour urine sample for total protein will be obtained and evaluated
- 10. Three electrocardiograms (12-lead ECGs) will be performed at screening after at least a 10-minute rest. If there is any clinically meaningful abnormality observed based on the investigators judgment for the first ECG test, the other 2 additional ECG tests will be requested at least 5 minutes apart and all 3 test results should be recorded. If the clinically meaningful abnormality was observed in 2 of 3 ECG tests, the patient is not eligible for this study. It is not required to conduct 3 ECG tests for all patients at

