4.1.3 Follow-up for Toxicities

When treatment is interrupted or permanently discontinued due to an AE or abnormal laboratory value, the patient must be followed at a frequency as medically indicated until resolution or stabilization of the event, whichever comes first. All patients will be followed for AEs and SAEs for at least 30 days following the last dose of pamiparib.

For prolonged hematological toxicities, treatment should be interrupted and blood counts should be monitored weekly until recovery. If the levels have not recovered to NCI-CTCAE \leq Grade 1 or baseline after 8 weeks, the patient should be referred to a hematologist for further investigations, including bone marrow analysis and blood sample for cytogenetics. If MDS/AML is diagnosed, treatment of pamiparib must be permanently discontinued, and the event should be reported as an SAE regardless of causality.

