7.3.1 Laboratory Evaluation

Laboratory assessments should be performed at a local certified laboratory on Day 1 before pamiparib administration. Laboratory assessments need not be repeated on Day 1 if these assessments were completed for screening within 96 hours of the first administration. Required assessments are listed in Appendix 2.

Clinical chemistry, hematology, and urinalysis will be performed at the time points specified in Table 5 for Phase 1, and Table 7 for Phase 2.

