APPENDIX 4: BLOOD REQUIREMENTS

Time point	Assessment	Total blood volume (mL)
		·
Phase 1		
Screening	Clinical chemistry	5
Screening	Hematology	2.5
	Coagulation	3
	Blood collection for BRCA mutation testing	8
	CA-125 ⁶	4
	Total	22.5
Cruele 1		22.5
Cycle 1	Clinical chemistry	5
Day 1	Hematology	2.5
	Coagulation	3
	Pharmacokinetics ¹²	16 ²
	Total	26.5
Day 2 to Day 22	Clinical chemistry	10
Day 2 to Day 23	Hematology	5
		6
	Coagulation Pharmacokinetics ¹²	20 ²
Carala 2	Total	41
Cycle 2	Clinical chamister	5
Day 1 to Day 21	Clinical chemistry	2.5
	Hematology	3
	Coagulation	42
	Pharmacokinetics ¹²	
 	Total	14.5
Cycle 3 Day 1 to Day 21	Clinical chemistry	5
Day 1 to Day 21		2.5
	Hematology Coagulation	3
	Pharmacokinetics ¹²	42
		4
	CA-125 ⁶	18.5
Sub	Total	
Subsequent cycles	Clinical chamister	5
Day 1	Clinical chemistry	
	Hematology	2.5
	Coagulation	3
	Total	10.5

EOT	Clinical chemistry	5
	Hematology	2.5
	Coagulation	3
	Total	10.5
Other blood samples ^{3 4,5}		

1 Unscheduled blood samples for pharmacokinetic analysis may also be collected whenever any notable safety is seen, to evaluate if the observation is exposure related.

- 2 Cannulation for blood sampling for pharmacokinetics will be performed. Blood will be collected via the intravenous cannula pre-dose and at the time points specified in Table 6 for Phase 1 Portion, Table 8 for Phase 2 Portion.
- 3 Blood samples (4 mL) should be obtained, when possible, for analysis of plasma pamiparib in the event of a DLT.
- 4 Should a drug-drug interaction between pamiparib and a concomitant medication be suspected, further blood samples for PK analyses may be taken to characterize the extent of the interaction.
- 5 Additional blood PK samples will be taken to determine the plasma concentration of BGB-290 if there is an intra-patient dose escalation. The Investigator must record the time points for PK sampling and the time of dose administration before PK sampling in eCRFs.
- 6 For patients with ovarian cancer, fallopian tube cancer or primary peritoneal carcinoma, plasma CA-125 should be monitored every 6 week ± 7 days in the first year and every 12 weeks ± 7 days thereafter in the local laboratory in Phase 1 study.

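### Section 1.6 promises monthly haematological monitoring, but Table 5 moves Phase 1 haematology visits to every 12 weeks after Year 1 while pamiparib continues

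*Protocol*

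**What the plan says.** Protocol section 1.6 describes MDS and AML as a recognised risk of PARP inhibition and then says patients in this study will be "monitored monthly for hematological toxicities and reports of MDS and AML will be reported as SAEs". Nothing there restricts this to Phase 2 or to the first year.

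Section 7.3.1 says where the timing is set: "Clinical chemistry, hematology, and urinalysis will be performed at the time points specified in Table 5 for Phase 1", with Table 7 serving Phase 2. In Table 5, haematology is marked in the column for Cycle 4 onward and has no interval of its own. The column header reads "every 21 days for 1 cycle in Year 1, every 12 weeks ± 7 days thereafter". Study drug is shown as continuous, and section 4.1.1.3 sets no fixed end to treatment.

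Two further Phase 1 texts bear on frequency. Table 5 footnote 6 states: "All assessments, unless stated otherwise, must be performed before investigational product administration in each cycle". Appendix 4 budgets 2.5 mL for haematology on Day 1 of later cycles with no reduction after Year 1. The only 12-week step-down it mentions is for the tumour marker: "plasma CA-125 should be monitored every 6 week ± 7 days in the first year and every 12 weeks ± 7 days thereafter".

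**The concern.** The monthly monitoring is the safeguard that section 1.6 sets beside the MDS/AML risk. A site that follows Table 5, as section 7.3.1 tells it to, would not deliver that monitoring to a Phase 1 patient still on pamiparib in the second year. At stake is how soon a late cytopenia without symptoms would be picked up in such a patient. No efficacy estimate depends on it.

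**Working it through.** The plan gives no figure to reproduce. The check is interval arithmetic, followed by a search for any rule that would close the gap.

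**1. Interval.** Inputs: 12 weeks ± 7 days (Table 5 header), 21-day cycles, and the SAP 6.2.2 conventions of 30.4375 days per month and 365.25 days per year.
- Nominal gap: 12 × 7 = 84 days; 84 / 30.4375 = 2.76 months; 84 / 21 = 4 dosing cycles.
- Window counted from the previous visit: 84 ± 7 = 77 to 91 days, or 2.53 to 2.99 months.
- Window on a fixed grid: 84 ± 14 = 70 to 98 days, or 2.30 to 3.22 months. The protocol does not say which applies.
- Under the header, even the shortest gap is more than twice a month.

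**2. Scheduled counts per patient-year.**
- Header: 365.25 / 84 = 4.35.
- Monthly: 12. Shortfall 12 − 4.35 = 7.65, about 8.
- Per cycle: 365.25 / 21 = 17.39. Shortfall 17.39 − 4.35 = 13.04, about 13.

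**3. Does another rule supply the missing counts?**
- Table 5 footnote 7 says "these assessments will be conducted as frequently as the physician feels needed until toxicity resolves", but only after neutropenia, thrombocytopenia or a Grade 3 or higher chemistry toxicity has been found.
- The weekly counts in section 4.1.3 begin with a prolonged toxicity. In Table 9, weekly counts cover the first three cycles and then continue only for anaemia of Grade 2 or higher.
- Table 5 footnote 6 can be read as requiring a count every cycle, or only as placing assessments before the dose. It also yields to anything stated otherwise, which the header does.
- Appendix 4 is a blood-volume table.
- SAP 6.5.4 describes chemistry as done on Day 1 of each cycle, and protocol section 7.3.2 says much the same of ECOG status. Both items share the Table 5 column with haematology, but neither text sets a haematology interval.
- Table 7 keeps 21-day visits in Phase 2, so Phase 2 meets the monthly statement.

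No text sets a routine Phase 1 count after Year 1 that overrides the header.

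**4. Reach.** Section 1.4.3 reports 15 Phase 1 patients at 25 September 2017. Among the 8 ovarian cancer patients with efficacy data, 2 partial responders were on treatment, together with "4 with stable disease (on treatment: n=4", so 2 + 4 = 6. Treatment in the 9 ovarian cancer patients had lasted 8 to 260 days, so none of those was past Year 1 at that date. Version 5.0 is dated 21 September 2018, 361 days later. A patient with a post-baseline scan was due it no earlier than day 42 − 7 = 35, and 35 + 361 = 396 exceeds 365. Any of the six still on drug when version 5.0 was issued was therefore past Year 1. SAP section 1 says a majority of Phase 1 patients had ended the study before version 2.0. A majority of 15 is at least 8, which leaves at most 7. The number affected is thus somewhere from 0 to 7 and is not documented.

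**The case against.** The strongest reply has three parts.

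*Section 1.6 is background prose.* It says monthly loosely, does not mention blood counts, and no schedule in the protocol is monthly. Section 7.3.1 names the operative source, so sites are not left guessing. It is true that sites have a source. But in Year 1 and in Phase 2 that source is tighter than monthly, so the loose wording does no harm there. Only in Phase 1 after Year 1 does the schedule fall short of what the benefit-risk section says.

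*Per-cycle counts were probably intended.* Table 5 footnote 6, Appendix 4, SAP 6.5.4 and section 7.3.2 lean that way, and the 12-week step matches the Phase 1 imaging and CA-125 interval. This stands: the header may be a drafting carry-over and not a choice. It would therefore be wrong to say that the documents fix a 12-week gap on any reading, because the per-cycle reading gives 21 days. It remains a reason to correct the header, since none of these texts overrides it.

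*Version 5.0 may not have governed Phase 1.* SAP section 1 refers to protocol version 1.1 for Phase 1 operation, and that version is not available here. This stands as a limit. However, the version 5.0 change summary records edits to Table 5 itself (pregnancy testing), so the table was still being maintained.

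**Conclusion.** The mismatch is real and minor. Section 1.6 says monthly. The Table 5 header gives a nominal 84 days, about 2.8 months, or about 4.3 scheduled counts a year against 12 or about 17. It applies only to Phase 1 patients on pamiparib beyond one year: a minority of the 15 reported, possibly none. Phase 2 and the primary analysis are not touched. The conclusion rests on version 5.0 as written and on 15 being the Phase 1 total.

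Three stronger readings are tempting and not supported:
- A reader might set the 84-day gap against the 8 weeks in section 4.1.3 and conclude that a cytopenia could outlast the referral limit unseen. That section says that if counts have not returned to Grade 1 or "baseline after 8 weeks, the patient should be referred to a hematologist for further investigations". The period most naturally runs after detection, with drug held and counts weekly. It does not limit undetected time on drug, so detection shares built on it would measure nothing the protocol defines.
- A reader might raise the ceiling on affected patients by using the upper end of the planned 14 to 18. Sections 1.4.3 and 1.5 report 15 patients with the Phase 2 dose confirmed, and nothing indicates later Phase 1 enrolment.
- A reader might infer a clinical risk from the 5 of 15 patients with related Grade 3 anaemia. Its timing is not given and no rate after Year 1 is stated, so the risk cannot be sized.

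**What to change.** Add one footnote to Table 5, or correct the column header, so that haematology is done at least monthly (for example every 21-day cycle) while a Phase 1 patient takes pamiparib after Year 1. The other assessments in that column can stay 12-weekly. If 12-weekly counts are intended, qualify section 1.6 and give the reason.

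The cost is about 8 (monthly) to 13 (per cycle) extra local counts per patient-year. At the 2.5 mL in Appendix 4 that is 7.65 × 2.5 = 19 mL to 13.04 × 2.5 = 33 mL a year, for at most a handful of patients. The analysis does not change.
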